Official title Clinical Characteristics and Outcomes Until 2 Years of Age in Preterm Infants With Typical Chest Imaging Findings of Bronchopulmonary Dysplasia: A Propensity Score Analysis

NCT number 04163822

Document date 2021.5.18

Bronchopulmonary dysplasia (BPD) is a common chronic respiratory disease in preterm infants. The increase in the survival rate of premature babies following the improvement of perinatal treatment and care has caused an increase in the incidence of BPD in recent years, which has seriously affected the quality of life of preterm infants. According to the consensus reached at the workshop sponsored by the National Institute of Child Health and Human Development (NICHD) in 2001, BPD was clinically defined based on oxygen dependency in preterm infants. However, the refined NICHD definition of BPD in 2018 emphasized imaging findings to support a diagnosis of lung parenchyma disease.

Fibrotic opacities and cystic changes on chest imaging [chest X-ray (CXR) or computed tomography (CT) scan] were considered typical findings in BPD patients. In patients with severe BPD, the presence of bubbles/cystic appearance on CXR after 28 days of life was reported to be an important factor, and typical imaging findings can predict a poor pulmonary outcome in BPD patients. BPD is associated with poor outcomes. Although many studies have been conducted on BPD, there are limited reports specifically evaluating the association of typical imaging findings with clinical characteristics and later outcomes in patients with BPD.

We hypothesized that BPD with typical imaging findings was likely to be a particular subgroup of this entity, with a unique etiology, clinical characteristics and prognosis. Therefore, we performed a retrospective cohort study using data from the Department of Neonatology, Children's Hospital of Chongqing Medical University (CHCMU), and the patients were followed by telephone. Eligible patients fulfilled the following three criteria simultaneously: (1) BPD diagnosis according to the 2001 NICHD consensus; (2) chest imaging examination (CXR or CT) in the first week after birth; and (3) hospitalization within the first 7 days after birth. Patients were excluded from the study if they met one of the following conditions: (1) major congenital malformations or laboratory-confirmed chromosomal abnormalities; (2) inadequate clinical data or missing chest imaging data; or (3) loss to follow-up.

Relevant data were retrospectively collected, including demographics [i.e., sex, gestational age, age at admission, birth weight (BW)], perinatal factors [i.e., pregnancy induced hypertension (PIH), CAM, cesarean section, prenatal glucocorticoid administration, respiratory distress syndrome (RDS), sepsis, PDA, 5-min Apgar score], management during hospitalization [i.e., surfactant administration, noninvasive and invasive mechanical ventilation (IMV), postnatal

glucocorticoid administration, packed red blood cell (PRBC) transfusion], complications during hospitalization [i.e., IVH, retinopathy of prematurity (ROP), NEC], and outcomes. Primary outcomes were the severity of BPD, HOT at discharge, and mortality between 28 days after birth and 2 years of age. Secondary outcomes were (1) duration of hospital stay; (2) duration of oxygen supplementation; (3) routine physical assessment; (4) wheezing disorders; and (5) clinical visits and rehospitalizations for a respiratory reason between discharge and follow-up. The long-term outcomes were evaluated until 2 years of age.

Statistical Analysis

Statistical analysis was performed using SPSS 26.0. We used the Shapiro-Wilk test to analyze the normality of the data distribution. Variables without normal distributions were analyzed using the Wilcoxon-Mann-Whitney test and are reported as medians [interquartile ranges (IQRs)]. All normally distributed variables were analyzed using a t-test for comparisons of two independent groups and are presented as the means \pm standard deviations. Categorical variables were analyzed using the chi-square test or Fisher's exact tests and are reported as the numbers (%) of subjects. To further evaluate the associations between typical chest imaging findings and the primary and secondary outcomes, a propensity score analysis with 1:1 matching was performed. The following covariates were included based on previous studies: GA, BW, cesarean section, CAM, PIH, sepsis, RDS, PDA, prenatal glucocorticoid administration, postnatal glucocorticoid administration, NEC, IVH, RSD, IMV \geq 7 days, \geq 2 PRBC transfusions. The nearest neighbor matching method was used to select each matched pair by using calipers with a width equal to 0.01 of the standard deviation of the logit of the propensity score. Typical chest imaging findings and the above 15 covariates were analyzed for collinearity and incorporated into the multivariate binary regression model, and the forward likelihood ratio (LR) was used to select the variables to further determine the independent factors of BPD infant mortality. A p-value < 0.05 was considered statistically significant.

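### No birth window is stated and calendar period is in neither the propensity score nor the mortality model, so a time trend, if there was one, would go unadjusted

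*Combined protocol and SAP*

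**What the plan says.** The unnumbered opening paragraph of the combined protocol and SAP says of BPD in recent years: "The increase in the survival rate of premature babies following the improvement of perinatal treatment and care has caused an increase in the incidence of" the condition. It gives no dates or figures and speaks of preterm infants in general.

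The design paragraph reads "we performed a retrospective cohort study using data from the Department of Neonatology" of one children's hospital. On eligibility it says: "Eligible patients fulfilled the following three criteria simultaneously: (1) BPD diagnosis according to the 2001 NICHD consensus". The other two criteria concern imaging and admission in the first week of life. None limits the calendar date of birth or admission.

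The data-collection paragraph begins with "demographics [i.e., sex, gestational age, age at admission, birth weight (BW", then moves to perinatal factors, management, complications and outcomes. No date or year of birth is named. Home oxygen therapy (HOT) at discharge and mortality from day 28 to 2 years are among the primary outcomes. Respiratory rehospitalization is secondary.

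Under Statistical Analysis, the propensity score covariates are "GA, BW, cesarean section, CAM, PIH, sepsis, RDS, PDA, prenatal glucocorticoid administration, postnatal glucocorticoid administration, NEC, IVH, RSD", followed by invasive ventilation for at least 7 days and "\geq 2 PRBC transfusions". On matching: "The nearest neighbor matching method was used to select each matched pair by using calipers with a width equal to 0.01 of the standard deviation" (that is, of the score on the logit scale). The mortality regression takes the imaging finding and the same 15 covariates as candidates and selects among them by forward likelihood ratio (LR).

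**The concern.** Calendar period can confound a retrospective comparison. Discharge on home oxygen is partly a matter of practice. The use of CXR or CT, and the readiness to report a finding as typical, may also drift. The background itself notes that the 2018 definition gave imaging more weight than the 2001 consensus did.

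If infants with typical findings cluster in one part of the birth window, and outcomes differ between the parts, the matched comparison mixes imaging with time of birth. A balance table confined to the 15 listed covariates would not reveal this. At stake is the interpretation of the HOT, mortality and rehospitalization comparisons, and of imaging as an independent factor for mortality.

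**Working it through.** **Step 1: search of the plan.** The covariate list has 15 entries, which agrees with the stated number if "RSD" is counted separately from "RDS". None is a year, period or date. Matching uses the score alone, with no restriction or stratification by period. The mortality model adds only the imaging finding, which makes 16 candidates. No calendar limit appears in the eligibility criteria and no calendar variable in the listed data. The plan gives no sample size, event count or outcome rate, so it has no figure to reproduce.

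**Step 2: how large could the bias be?** Every rate in this step is an assumption. Take two eras of equal size and no imaging effect within either. Let t be the share with typical findings in an era and r the outcome risk.

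- P(early | typical) = t_early / (t_early + t_late)
- P(early | other) = (1 − t_early) / [(1 − t_early) + (1 − t_late)]
- Group risk = P(early) × r_early + P(late) × r_late

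Assume typical findings in 20% of infants early and 35% late, mortality 12% then 6%, and HOT 20% then 45%.

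- P(early | typical) = 0.20 / 0.55 = 0.364
- P(early | other) = 0.80 / 1.45 = 0.552
- Mortality, typical: 0.364 × 12% + 0.636 × 6% = 8.2%
- Mortality, other: 0.552 × 12% + 0.448 × 6% = 9.3%
- Mortality OR = (0.0818 / 0.9182) / (0.0931 / 0.9069) = 0.87
- HOT, typical: 0.364 × 20% + 0.636 × 45% = 35.9%
- HOT, other: 0.552 × 20% + 0.448 × 45% = 31.2%
- HOT OR = (0.3591 / 0.6409) / (0.3121 / 0.6879) = 1.24

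With the imaging trend reversed (35% early, 20% late), P(early) is 0.636 for typical and 0.448 for other. The ORs become 1.14 for mortality and 0.80 for HOT. The direction of bias therefore depends on unknown trends.

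**Step 3: a range of settings.** Here the early-era share in each group is assumed directly. The entries are spurious ORs, again with no true imaging effect.

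| Risk early / late | Early share 50% / 50% (typical / other) | 55% / 45% | 60% / 40% | 70% / 30% |
|---|---|---|---|---|
| 10% / 10% | 1.00 | 1.00 | 1.00 | 1.00 |
| 12% / 8% | 1.00 | 1.05 | 1.09 | 1.20 |
| 15% / 7.5% | 1.00 | 1.08 | 1.16 | 1.35 |
| 20% / 5% | 1.00 | 1.15 | 1.32 | 1.75 |

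The first row and first column show that the bias vanishes if outcome risk does not differ by era, or if the era mix is the same in both groups. With an assumed 100 infants per group, the chance of a significant result in the spurious direction is 3% to 10% in the 12% / 8% and 15% / 7.5% rows where the shares differ. It reaches 25% only in the most extreme cell. The nominal rate in one direction is 2.5%.

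**Limit of the calculation.** These are crude mixtures without matching on the 15 covariates. They show what an unadjusted era difference could do, not what remains after matching.

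**The case against.** A reader might infer that, because the background describes changing survival and BPD incidence, era effects are in fact being attributed to imaging. The documents do not support that, for four reasons.

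1. No birth window is given. Follow-up to 2 years of age does not imply a wide one: a single year's births can be followed to age 2.
2. The background sentence is a general trend in other quantities. Every cohort member already has BPD under one fixed definition, and mortality counts from day 28. A rise in preterm survival or BPD incidence is not evidence of a change in later mortality, HOT practice or typical findings within this cohort.
3. If typical findings did not vary with birth year after adjustment, pairing infants born years apart would add noise but no bias.
4. Prenatal and postnatal glucocorticoids, prolonged invasive ventilation and repeated transfusion are already in the score. They may absorb part of a change in practice.

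All four points stand, and they make the bias conditional. They do not remove the gap. Nothing in the plan prevents pairing across birth years, and without the window a reader can neither rule the problem in nor rule it out. No covariate represents imaging modality or discharge policy on home oxygen. Surfactant and noninvasive ventilation are collected but are not in the score.

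**Conclusion.** The omission is certain; its consequence is not. Bias arises only if births span several years and both typical findings and outcomes shifted over that span after adjustment for the 15 covariates. The documents do not show that these conditions were met, so the stronger claim that the results are confounded by era should not be made.

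The main illustration gives ORs of about 0.80 to 1.24 where the truth is 1.00. The wider grid runs from 1.00 to 1.75, with the upper end needing a fourfold risk difference between eras and a 70% / 30% split. Rehospitalization was not illustrated numerically, but the same reasoning applies. This is a worthwhile, inexpensive improvement rather than a demonstrated flaw.

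**What to change.** - State the first and last dates of birth (or admission) of the cohort.
- Add year of birth to the propensity score, as a linear term or a few bands suited to the window, and report its standardized difference after matching.
- Force the same term into the mortality regression, for instance in a first block before forward LR selection runs on the rest. Otherwise the selection can drop it.
- If the window is only a year or two, reporting birth-year balance is enough.
- Use exact matching within birth bands at most as a sensitivity analysis. With a caliper already at 0.01 SD of the logit, it could lose an unknown number of pairs.

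**Cost.** The change needs some SAP wording and one variable that should be in the chart, since age at admission and follow-up to 2 years both depend on the date of birth. It adds one or a few terms to each model and may lose some pairs. In the mortality model, with 16 candidates already and the number of deaths unstated, several band terms would cost precision, so a linear term is the lighter choice where it fits.

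### The image that classifies an infant is neither identified nor dated, so deaths from day 28 and in-hospital covariates cannot be ordered against the exposure

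*Combined protocol and SAP*

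**What the plan says.** The document has few headings, so places are named by content.

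- **Exposure (background).** Typical findings are described by appearance only: "Fibrotic opacities and cystic changes on chest imaging [chest X-ray (CXR) or computed tomography (CT) scan] were considered typical findings in BPD patients". No age, window or index image is attached.
- **Imaging times.** Two appear. One is the eligibility criterion "2) chest imaging examination (CXR or CT) in the first week after birth". The other is in the background: "In patients with severe BPD, the presence of bubbles/cystic appearance on CXR after 28 days of life was reported". The second reports earlier work and is not adopted as a study rule. The first is not said to classify anyone.
- **Exclusions.** Infants are removed for "inadequate clinical data or missing chest imaging data"; which image must be missing is not stated.
- **Outcomes.** "Primary outcomes were the severity of BPD, HOT at discharge", together with "mortality between 28 days after birth and 2 years of age".
- **Analysis (Statistical Analysis).** 1:1 propensity matching is used to "evaluate the associations between typical chest imaging findings and the primary and secondary outcomes". Mortality is also analysed by binary regression with forward likelihood-ratio selection. Both use the same 15 covariates. In the data-collection paragraph, management and complications are dated only to the hospital stay, with no cut-off at any image.

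**The concern.** Typical imaging is the study's only exposure, and every matched comparison and the mortality model depend on it. A comparison of groups defined by an image needs three things in order: covariates up to the image, then the image, then the outcome. Here the outcome has a fixed start (day 28), the covariates have a period (the stay), and the exposure has no date.

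If the image comes after day 28, the death count opens before infants can be classified. If it comes before discharge, the analysis may match on events that happened after the exposure. A reader could not tell which of these affects the reported mortality association.

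**Working it through.** **Step 1. Ordering, from the text alone.**

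| Classifying image taken | Deaths counted from day 28 | Covariates from the hospital stay |
|---|---|---|
| First week | All follow the image | Can follow it |
| Later, up to day 28, before discharge | All follow the image | Can follow it |
| After day 28, before discharge | Some can precede it | Can follow it |
| After discharge and after day 28 | Some can precede it | Precede it |

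Only an image taken at or after discharge and no later than day 28 escapes both problems. The covariates at issue are postnatal glucocorticoid, NEC, IVH, invasive ventilation reaching 7 days and two or more red-cell transfusions. Gestational age, birth weight, cesarean section, PIH, CAM and prenatal glucocorticoid are fixed by birth and unaffected.

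**Step 2. Inputs for illustration.** The plan gives no sample size, event count or imaging rate, so it has no figure to reproduce. All values below are assumptions:
- e: mortality between day 28 and the usual image age, 0.01 to 0.05
- m: later mortality, 0.05 or 0.10 (one example below also takes e = 0.10 in one group)
- f: share of those early deaths that precede the image, 0.1 to 0.25
- p: share of infants who would show typical findings, 0.4 or 0.6

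**Step 3. Infants without the image are excluded.** True risk from day 28 is e + (1−e)m. Observed risk is [e(1−f) + (1−e)m] / (1−ef).

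*Absolute risk.*
- e = 0.01, m = 0.10, f = 0.1: true 0.109; observed 0.108/0.999 = 0.1081; understated by 0.8% (relative).
- e = m = 0.05, f = 0.25: true 0.0975; observed 0.0850/0.9875 = 0.0861; understated by 11.7%.

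*Ratio, no true effect.*
- Equal f: 1.00.
- e = m = 0.05, f = 0.25 in one group and 0 in the other: 0.0861/0.0975 = 0.88, or 1.13 if reversed.

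*Ratio, true effect, f = 0.25 in both groups.*
- e = 0.10 vs 0.05, m = 0.05: true 0.145/0.0975 = 1.49; observed (0.120/0.975)/(0.0850/0.9875) = 0.1231/0.0861 = 1.43.
- e = 0.05, m = 0.10 vs 0.05: true 0.145/0.0975 = 1.49; observed (0.1325/0.9875)/(0.0850/0.9875) = 0.1342/0.0861 = 1.56.

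So equal f does not protect the ratio once there is an effect, and the error can go either way.

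**Step 4. Infants without the image count as non-typical.** With no true effect, the non-typical risk is [(1−p)(e+(1−e)m) + pef] / [(1−p) + pef]; the typical risk is as observed in Step 3.
- e = 0.03, m = 0.05, f = 0.25, p = 0.4: 0.0715/0.0831 = 0.86.
- e = m = 0.05, f = 0.25, p = 0.6: 0.0861/0.1141 = 0.75.

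The direction is downward because pre-image deaths fall only in the non-typical group.

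**Step 5. Precision cost of a later start.** The share of deaths after day 28 that fall before the landmark is e/[e+(1−e)m]. The standard error of the log risk ratio grows by about 1/√(1−share).
- e = 0.01, m = 0.10: 0.01/0.109 = 9.2%; factor 1.05.
- e = m = 0.05: 0.05/0.0975 = 51.3%; factor 1.43.

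**The case against.** The strongest reply is that the text points to exclusion. A first-week image is already required for entry, so a separate exclusion for missing imaging most naturally removes infants who lack a later, classifying image. On that reading, with no effect and equal pre-image shares of deaths, the ratio is 1.00. If the first-week image classifies, no counted death can precede it. These points stand, and they limit the claim.

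Three stronger readings are tempting, and the documents support none of them.

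- A reader might infer that the plan biases the mortality ratio downward. That requires unimaged infants to be counted as non-typical, which nothing in the document says. Step 4 shows what that rule would do, not what the plan does.
- A reader might attach a size to the bias. The result follows the assumptions: if 30% to 70% of deaths are assumed to precede the last classifying image, simulation under the Step 4 rule with no effect gives 0.54 to 0.80, lower than most results with smaller shares. None of these is an estimate for this study.
- A reader might say that covariate timing and aim are missing altogether. They are not. Some covariates are fixed by birth, others are dated to the stay, and an associational aim is stated. What is missing is timing relative to the image.

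The reply does not restore the ordering. Exclusion still understates absolute mortality and distorts a non-null ratio, and a first-week image still leaves postnatal covariates able to follow the exposure.

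**Conclusion.** The point holds in a limited form and should be fixed. That no classifying image or age is stated is certain. Because the day-28 start and the stay-long covariates are stated, at least one of them can be out of order with the exposure on essentially any choice of image, so this is more than a missing detail.

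The consequence is conditional. With exclusion after a late image, day-28 mortality is understated (0.8% to 11.7% relative in the two cases shown), and the ratio can be relied on only under no effect with equal pre-image shares. With an image before discharge, the covariate problem arises; no size is claimed for it. All figures rest on assumed rates, and the actual bias cannot be determined from the documents.

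**What to change.** 1. State one index-image rule and one classification window for all infants, with the ages set and justified by the investigators, and say how infants without an index image are handled.
2. For the exposure comparison, count mortality from the end of the window (a landmark). Keep mortality from day 28 to 2 years as a descriptive result, and report pre-landmark deaths and unimaged infants by number and characteristics.
3. In the propensity score and the mortality regression, use only covariates dated on or before the index image. The cut-off is the image, not the end of the window. It applies whether the target is a total association or what imaging adds beyond illness severity, since later events are unknown at imaging and can be recorded only in infants who live long enough. Report the whole-stay covariate set as a sensitivity analysis only.

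**Cost.** Dates of images, deaths and covariates must be re-abstracted from existing records; no new imaging is needed. Deaths between day 28 and the landmark leave the comparison, which raises the standard error of the log risk ratio by about 5% to 43% on the assumed rates; a shorter window reduces this. The landmark ratio also answers a narrower question, about deaths after the window. In the two examples with a true effect it would be 0.05/0.05 = 1.00 and 0.10/0.05 = 2.00, not 1.49, so it should be labelled as such. If sicker infants are more likely to be imaged, the imaged group is selected, which is a further reason to describe those without an image.

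### Excluding infants lost to follow-up from the whole study discards outcomes normally known by discharge and makes the mortality set depend on later reachability

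*Combined protocol and SAP*

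**What the plan says.** The document has few headings, so places are named here by content.

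- **Exclusion criteria.** The rule acts on the whole study: "Patients were excluded from the study if they met one of the following conditions". The conditions include "2) inadequate clinical data or missing chest imaging data; or (3) loss to follow-up". Inadequate clinical data and loss to follow-up are thus separate grounds for removal. Loss to follow-up is not defined.
- **Design.** The cohort is retrospective, and "the patients were followed by telephone".
- **Outcomes.** "Primary outcomes were the severity of BPD, HOT at discharge, and mortality between 28 days after birth and 2 years of age". Secondary outcomes include hospital stay, "duration of oxygen supplementation", routine physical assessment, wheezing disorders, and "clinical visits and rehospitalizations for a respiratory reason between discharge and follow-up".
- **Statistical Analysis.** "a propensity score analysis with 1:1 matching was performed", with a caliper of 0.01 of the standard deviation of the logit of the propensity score. Mortality is also modelled by binary regression with forward selection. The section gives no censoring, bounds, report of loss or comparison of lost with retained infants.

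**The concern.** Whether an infant can be reached by telephone is settled after discharge. Using it as a condition of entry has two consequences.

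First, an infant removed only for loss to follow-up has passed the separate test of adequate clinical data. That infant would normally have a recorded HOT status at discharge and length of stay, and probably a BPD grade, although the time of grading is not stated. Removing the infant from those analyses gains nothing. It also takes a candidate out of a 1:1 match with a very narrow caliper.

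Second, the set in which mortality from day 28 to 2 years is counted is selected on a later event. If deaths before discharge always stay in while some infants discharged alive drop out, the proportion who died changes even when the lost infants fare no differently from other discharged infants. If loss, or the prognosis of the lost, differs between imaging groups, the comparison that the study is about shifts as well. Because the plan does not ask for loss to be reported by group, a reader could not tell whether the effect is trivial.

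**Working it through.** The plan states no loss rate, death rate, event count or sample size, so it has no figure to reproduce. Every rate below is an assumption chosen to show direction and scale.

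**Symbols.** h = death from day 28 to discharge; p = post-discharge death in reached infants; l = share of infants discharged alive who are lost; k = death risk in lost infants divided by that in reached infants. In-hospital deaths are assumed never to be lost.

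- True mortality = h + (1−h)·p·(1 − l + l·k)
- Mortality after the exclusion = [h + (1−h)(1−l)p] / [h + (1−h)(1−l)]
- Subtracting: observed − true = (1−h)·l·(observed − k·p)

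The last line gives the direction without any assumed rates. The bias is upward when lost infants die at less than the retained-cohort risk, downward when they die at more, and zero when the two are equal.

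**Mortality, h = 5%, p = 3%, k = 1.** True risk = 0.05 + 0.95 × 0.03 = 7.85%. At 5% loss the observed risk is (0.05 + 0.95 × 0.95 × 0.03) / (0.05 + 0.95 × 0.95) = 0.077075 / 0.9525 = 8.1%.

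| Loss among infants discharged alive | Observed mortality |
|---|---|
| 2% | 7.9% |
| 5% | 8.1% |
| 10% | 8.4% |
| 20% | 9.0% |
| 30% | 9.8% |

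The break-even is k = observed/p: 2.7 at 5% loss and 3.0 at 20%. Above it, mortality is understated. With h = 0 and k = 1 there is no bias.

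**Imaging contrast, no true effect, k = 1 in both groups.**

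| Loss, typical v other | Odds ratio seen (true 1.00) |
|---|---|
| equal | 1.00 |
| 2% v 5% | 0.98 |
| 5% v 10% | 0.97 |
| 10% v 20% | 0.92 |
| 10% v 30% | 0.84 |
| 30% v 10% | 1.19 |

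Varying h over 2–8% and p over 1–5%, 5% v 10% loss gives 0.95–0.98, and 10% v 30% gives 0.79–0.92.

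Equal loss protects the contrast only if prognosis among the lost is also similar. Take 20% loss in both groups, with k = 4 in one and k = 1 in the other. True risks are 0.05 + 0.0285 × (0.8 + 0.8) = 9.56% and 7.85%. That is a true odds ratio of (0.0956/0.9044) / (0.0785/0.9215) = 1.24, seen as 1.00.

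With a real difference (h = 10% v 5%, p = 3%, k = 1), a true odds ratio of 1.71 reads 1.72 at 5% equal loss and 1.76 at 20%.

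**HOT at discharge, assumed 30% of infants discharged alive.** If loss is unrelated to HOT, the estimate stays 30.0% and its standard error grows by 1/√(1−l): about 3% at 5% loss and 12% at 20%. If 5% of infants with HOT and 10% of those without are lost, HOT reads 0.285/(0.285 + 0.63) = 31.1%. At 10% and 20% it reads 0.27/(0.27 + 0.56) = 32.5%. The HOT odds ratio is unchanged if the pattern is the same in both imaging groups. It is multiplied by 0.95/0.90 = 1.06 or 0.90/0.80 = 1.13 if the pattern occurs in one group only.

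**Bounds on mortality** (all lost infants survive, or all die). Lower = h + (1−h)(1−l)p; upper adds (1−h)l. This gives 7.8–9.7% at 2% loss, 7.7–12.5% at 5% and 7.3–26.3% at 20%. With equal true risk and 5% loss in each group, the extreme odds ratios are (0.1246/0.8754)/(0.0771/0.9229) = 1.70 and its inverse, 0.59.

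**The case against.** The strongest reply is that nothing shows the effect to be material. At modest loss the contrast barely moves, at equal loss with similar prognosis a null effect stays null, and the study's aim is the imaging association, not absolute mortality. That stands, and it limits how strongly the point can be put.

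Two premises are inferences. The documents do not say that HOT and stay were kept for excluded infants. The separate exclusion for inadequate clinical data makes it likely, no more. Nor do they say that follow-up begins at discharge. The phrase "clinical visits and rehospitalizations for a respiratory reason between discharge and follow-up" belongs to one secondary outcome, and the mortality window opens at day 28. That in-hospital deaths cannot be lost is therefore an assumption, and the mortality figures rest on it.

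A reader might infer that the exclusion must hide deaths, or that it invalidates the imaging comparison. The documents support neither: the bias can run either way or be nil, and no loss figure is given.

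A reader might also infer that mortality must be rebuilt as a Cox model from day 28, that HOT needs a composite with in-hospital death, or that oxygen duration needs a competing-risk analysis. These go beyond the defect. The exclusion does not remove in-hospital deaths (on the assumption above). A day-28 origin needs exposure and covariate timing that the plan does not give. The oxygen method is a separate, debatable choice. It is true that "Variables without normal distributions were analyzed using the Wilcoxon-Mann-Whitney test" and that such a test cannot use censored durations, but analysing reached infants avoids that.

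What the reply does not answer is that the rule, as written, discards discharge-based data for no benefit and leaves loss undefined and unreported.

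**Conclusion.** The point holds as a cheap improvement. The scope of the exclusion is clear from the text, and nothing elsewhere narrows it. For HOT at discharge, hospital stay and probably BPD severity, the sure cost is precision and match partners; bias arises only if loss is related to the outcome. For mortality, the direction depends on how the risk in lost infants compares with the retained-cohort risk, given that in-hospital deaths are captured in the chart. The imaging contrast is at risk mainly when loss, or the prognosis of the lost, differs by group.

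The actual size is unknown. Under the assumed rates the distortion of a null odds ratio is slight at 5% v 10% loss and appreciable only when loss is both large and uneven, as at 10% v 30%. Confidence is medium: the rule is certain, its effect is not.

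**What to change.** 1. Delete loss to follow-up as a study-level exclusion. Define it (for example, vital status at 2 years unknown) and report the number lost by imaging group.
2. Match from all otherwise eligible infants. In that matched set analyse BPD severity, hospital stay, and HOT at discharge among infants discharged alive.
3. For mortality, keep the planned binary analysis in infants with known 2-year vital status. Add one sensitivity analysis that includes lost infants: time to death censored at last contact, with best- and worst-case bounds on the group contrast. State the time origin. Censoring alone does not deal with informative loss, which is why the bounds are needed.
4. Analyse outcomes that need telephone data (wheeze, visits, rehospitalization, and oxygen duration where it runs past discharge) in reached infants of the matched set, and report their covariate balance.

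**Cost.** New SAP wording and a re-run of the matching. Chart data and last-contact dates for the excluded infants may have to be re-extracted, since the documents do not say they were kept. No new recruitment is needed. Some matched pairs will be broken wherever follow-up is required, and the main mortality analysis still rests on infants with known status, so the selection is made visible and bounded but not removed. If loss is large the bounds will be wide and may settle little.
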